### 7.2 Health Economic Analysis

Resource use will be measured using the Child and Adolescent Service Use Schedule (CA-SUS) (Beecham & Knapp, 1992, 2001). The measure is self-reported by parents in interview and has been successfully applied in many previous economic evaluations. Health and social care resource use will be costed using nationally applicable unit costs from standard sources (e.g. NHS reference costs for hospital episodes, British National Formulary for medication and PSSRU Unit Costs of Health and Social Care for community services). In addition, our group has access to a wide range of education sector unit costs from a variety of sources, including directly calculated as well as publicly available costs. The cost of the new personalised intervention will be directly calculated, using a micro-costing approach, based on data collected from therapists and clinical records.

The economic evaluation will be carried out from an NHS/Personal social services perspective as recommended by NICE, and a cost-consequences analysis will also be undertaken from a societal perspective and will focus on costs and parental and child quality of life outcomes measured within the period of study (up to 16 weeks). The economic analysis will be conducted within a cost-utility and cost-consequences framework with the former estimating the programme incremental cost per quality adjusted years of life (QALYs) gained for both parents and children over the trial follow-up period. Parental QALYs will be estimated through administration of the self-complete EQ5D measure and for children using the recently developed CHU-9 instrument.

The economic analysis will also evaluate the within-trial resource impacts from a wider societal perspective (e.g. inclusive of costs to the education system) and will also seek to translate any observed improvement in behavioural outcomes over trial follow-up into estimates of long-term resource savings to public sector organisations. An existing decision analytic model published by Bonin et al (2011) will be used as a basis for exploring the long-term public sector resource impacts linked to any improved behavioural outcomes observed within the trial. This secondary economic analysis will be used to assess the sensitivity of the estimated difference in overall cost of service use between intervention and controls to inclusion of wider and longer-term resource impacts.

We will employ standard methods of statistical analysis to evaluate programme cost-effectiveness, including multiple imputation for missing data (dependent on the nature and extent of the missing data) and parametric tests for differences in costs, with covariates for pre-specified baseline factors and the robustness of the parametric tests confirmed using bias-corrected, nonparametric bootstrapping. Conclusions regarding intervention cost-effectiveness will be assessed using varying assumptions regarding the maximum incremental cost per QALY threshold for determining programme value for money (using the existing cost-effectiveness threshold adopted by NICE as the "base-case"). We will also evaluate statistical uncertainty around the estimated mean programme incremental cost per QALY by evaluating the probability that the intervention will be cost-effective across varying assumed threshold values.

#### 7.3 PROCESS EVALUATION

## Qualitative process evaluation analysis

The primary aims of the process evaluation analysis are to understand the parents' experiences of the Parent-led Education and Support (PLES) intervention and the Personalised Programme for Children and Parents (PPCP) intervention, assess the feasibility of delivering both interventions, and to examine the real-life processes of intervention fidelity.

#### Parent Interviews

Semi-structured interviews will be conducted with 15 to 20 subjects from each arm of the trial or at data saturation if sooner, when the intervention and follow-up assessments have been completed. Additional signed consent is not required as participants have already consented to being interviewed and recorded when first recruited to the study. Interviews will be conducted using a topic guide, but the researcher will be responsive to issues emerging from parents' accounts. Interviews will be conducted in-person or via zoom, whichever is most convenient for the parent, audio-recorded and transcribed verbatim.

Participants will receive a new information sheet to inform them of the additional interview, and to invite them to take part. They will also be informed that if they do decide to participate in the qualitative interview, they will receive an additional payment in the form of vouchers to the value of £50.

The Qualitative Research Associate will provide training, supervision and support to the Researchers engaged in delivering and coding the interviews.

# **Trial Therapist Interviews**

The five clinicians in the PPC study – three PPCP and two PLES – will be interviewed by the Qualitative Research Associate to examine their experiences of the process of both interventions from development to implementation. (The interview guide has been added to the study checklist). Interviews will be conducted over zoom at a time most convenient for the clinician, audio-recorded and transcribed verbatim. The Qualitative Research Associate will undertake a reflexive thematic analysis and the Researchers will be involved in checking the transcripts as an additional way to increase their skillset across the project.

#### 8. STUDY SETTING

Potential participants will be identified from the parents or carers of children referred to Parent Training Groups funded and/or delivered by a local authority or NHS at participating sites in North London, South London and Berkshire. Recruitment and data collection will take place at all three sites. Parents who have participated in parent training groups but their children still show high levels of behaviour problems, or those who for whatever reason cannot engage in a group approach will be invited to

take part in the RCT. All CAMHS sites are fully equipped with staff experienced in treating and researching child conduct problems and possess the necessary facilities to conduct this research. For example, all sites have the appropriate rooms for consultations, meetings, individual and group treatment, and suitable toys and books for children.

# 9. SAMPLE AND RECRUITMENT

# 9.1 Eligibility Criteria

#### 9.1.1 Inclusion criteria

- a) Aged 4 9 years
- b) With a minimum score on Parental Account of Children's Symptoms (PACS) scale of +1.3SD (i.e. top 10%) with a raw score greater than or equal to 1.32.
- c) (i) Having previously been referred to a Parent Training group using evidence based principles and either participated, dropped out or declined to attend or (ii) Known to Child and Adolescent Mental Health Services or Local Authorities or other community services managed by or working with public funded organisations who for whatever reason cannot engage in a group approach.

#### 9.1.2 Exclusion criteria

- a) Child has significant developmental delay.
- b) Parents have marked difficulty in understanding of spoken and written English so that assessment with standard research instruments is not possible.
- c) Parents lack the capacity to give informed consent to participate.
- d) Child has a confirmed diagnosis of autism spectrum disorder.
- e) Child is the subject of a Child Protection Plan.

#### 9.2 Recruitment

The primary pathway into the trial will be to identify families who have been offered, have attended, or are attending, Parent Training groups being delivered in North London, South London and Oxford for child behaviour problems. Parents who report that their child continues to show challenging behaviour will be targeted. Group facilitators will ask these parents if they would be interested to hear about a research project which is aiming to find out whether a new, individualised approach to child behaviour problems can be more helpful than a group-based approach. Parents will be given a brief introduction to the study and, if they express interest, the facilitator will ask for their permission to pass their contact details on to the study team. Parents who agree to hear more about the study will be contacted by the research team.

Researchers will ask parents to complete a screening questionnaire to determine whether their child's behaviour problems warrant inclusion in the trial. Researchers will also determine that both parent and child fulfil criteria for inclusion into the study, and that there are no criteria that exclude them from taking part. They will establish that the parent has capacity to consent on behalf of both themselves and the child. These parents and children will be invited to take part in the RCT.

A secondary pathway into the trial will be parents of children with significant behaviour problems who are currently in contact with local authorities, the voluntary sector, or CAMHS, who for whatever reason cannot engage in a group approach. They will be invited by their clinician/referrer in the same way as described above.

A poster/flyer targeting parents of children with behaviour problems will be distributed to those parents who wish to learn more about participating in the PPC RCT. Through a QR code on the poster, parents will be directed to a web-page hosted by the Tavistock & Portman NHS Trust, from which they can make their own decision about whether or not they wish the study to contact them. The web page will be easily accessible from their mobile phone. The poster will be sent to SENDCOs in schools, to clinicians in CAMHS NHS clinics and to practitioners of parenting groups. They can then circulate the flyers to parents they feel might benefit from participation in the trial. Parents can access the trial email and/or telephone number if they wish to make initial enquiries or if they are unable to use the QR code, without having to commit to taking part in the study. It is likely that many parents will prefer the opportunity to look at a website before committing themselves to participation, resulting in a more informed choice by parents. The onus on the clinician to "sign them up" is removed, making it easier to refer a larger number of families.

The flyer will also be posted on social media platforms such as Twitter, Facebook, and parenting forums. This will be a way of making the study available to the greatest number of parents who might benefit from the interventions that are offered.

#### 9.2.1 Size of trial sample

The trial aims to recruit and randomise 248 parent/child dyads. Half of the total number recruited (estimate 124) will be randomised to each arm of the trial. This sample size has been calculated on the basis of a PACS 16 week difference between the mean scores of the PPCP and waitlist groups of 0.4 standard deviations, based on an independent samples t-test with 80% power and alpha=0.05 (sample size required = 198), and is inflated for an anticipated 20% attrition rate (Scott et al 2001; Scott et al 2010). This is a conservative estimate, our previous trial with a clinical population got an effect size of 1.06 standard deviations compared to a wait list control (Scott et al 2001). A standardised effect size of 0.4 amounts to a PACS difference of 0.16 points. We consider such a difference clinically significant because any numerous studies it has been associated with clinically significant reduction in child aggressive and antisocial behaviour, improved school attendance and a happier family atmosphere. Also these improvements have been retained at longer term follow-up over several years (Scott et al 2014).

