# STUDY SUMMARY

Study Title	Personalised assessment and intervention packages for children with conduct problems in Child Mental Health Services.
Internal ref. no. (or short title)	PPC
Research Questions/Aims	
 
Conduct an RCT to evaluate the efficacy of a new intensive home-based intervention for children with conduct problems, called the Personalised Programme for Children and Parents (PPCP) which is an individual family approach which is adapted, or personalised, to the specific needs and circumstances of each family in comparison to a waiting list control group.
 
As a secondary analysis, to compare a less intensive intervention, the Parent-led Education and Support (PLES) which is a package of resources and support, against the waiting list.
 
A further secondary analysis is to compare the PPCP with the PLES. The specific research questions to be assessed are:         
 
Primary research question: (i) Is PPCP an effective intervention for persistent conduct problems?
 
Secondary research questions: (ii) Is the intensive
 
 
 

	PPCP intervention more effective than the low-level PLES intervention? (iii) Is the low-level intervention, PLES, effective? (iv) Are either of the two interventions cost-effective?
Study Participants	Parents of children aged 4 to 9 with significant conduct or oppositional difficulties who have been referred to structured parenting groups but have declined, dropped out or whose children have not responded and those who for whatever reason cannot engage in a group approach.
Planned Size of Sample (if applicable)	248 parent-child dyads
Follow up duration (if applicable)	Follow-up will be16 weeks and 32 weeks following the commencement of the intervention in each trial arm.
Planned Study Period	1 October 2022 – 31 August 2025 (delayed start due to Covid)

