#### 3.1 Objectives

Train NHS mental health professionals to deliver the personalized approach.

Conduct a full RCT to establish whether the personalized approach is superior to parent-led education and support for those for whom group parent training did not work and those who, for whatever reason, cannot engage in a group approach.

Assess the clinical efficacy of PPCP compared to no treatment (waiting list) and as a secondary comparison its relative efficacy when compared with the low-level intervention PLES, and the efficacy of PLES compared to no treatment (waiting list).

The cost-effectiveness of both interventions will be assessed using the child and adolescent service use schedule (CA-SUS).

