## 4.2 Revised Study Plan

In discussion with the funder it was decided to stop recruitment on 31st August 2024 despite not reaching the intended sample size. It was agreed to follow up participants to 16 weeks and then lock these data and analyse only the 16 week outcomes as part of the NIHR funder report. We will formally report on outcome differences between PPCP and waitlist arms at 16 weeks. 32 week outcomes will be collected beyond the end of the original funding period which was 31st April 2025; data will now be collected until 31st August 2025. By necessity future analyses of differences with PLES will not be blind. Depending on attrition rates it might also be only possible to provide descriptive analyses involving the PLES arm. However, the team is committed to ultimately publishing all outcome data collected as part of this study.

By the end of December 2024, we had recorded the outcomes of 80 trial participants at the 16-week-from-randomisation stage. This means that comparisons will be made between 40 participants who have completed the PPCP intervention and 40 participants who have been on the waiting list, which is the primary outcome objective.

[figure not shown]
However, in view of the revised sample size (numbers of participants being around 30-40% of those predicted) the study may be better described as a Pilot and Feasibility Study, rather than a full RCT.

NIHR has agreed a proposal to conduct two additional qualitative interviews exploring the experience of study participants and that of the practitioners in order to optimise learning for the NHS. These will be conducted and analysed as described in Section 7.3 Process Evaluation.

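### The Study Summary and section 9.2.1 still present 248 dyads and 80% power for 0.4 SD as current, but the 40 v 40 comparison in section 4.2 has about 42% power on the same test

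*Protocol*

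**What the plan says.** The Study Summary gives the planned size as "248 parent-child dyads". Section 9.2.1 says "The trial aims to recruit and randomise 248 parent/child dyads". It rests this on a "difference between the mean scores of the PPCP and waitlist groups of 0.4 standard deviations" and describes the calculation as "based on an independent samples t-test with 80% power and alpha=0.05 (sample size required = 198", inflated for 20% attrition. It adds that "A standardised effect size of 0.4 amounts to a PACS difference of 0.16 points" and regards a difference of that size as clinically significant. Neither place says that these figures have been superseded.

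Section 4.2 (Revised Study Plan) says that recruitment stopped on 31 August 2024 short of the intended size. By the end of December 2024, 80 participants had 16-week outcomes, so that "comparisons will be made between 40 participants who have completed the PPCP intervention and 40 participants who have been on the waiting list". The section undertakes to report the PPCP v waitlist difference formally. It then puts the numbers at around 30-40% of those predicted and says that "the study may be better described as a Pilot and Feasibility Study, rather than a full RCT".

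Section 7.1.1 handles the same change differently. It labels the mixed-model analysis as the original plan and then sets out its replacement, an ANCOVA with sex, age and the randomisation stratifier as covariates. Baseline PACS is not named among them.

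**The concern.** Two parts of one protocol version describe trials of different size, and only the larger has a stated power. A reader who relies on section 9.2.1 would take the primary comparison to have an 80% chance of detecting 0.4 SD, and would read a non-significant result as fair evidence against an effect of that size. The smaller trial does not support that reading.

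The result has consequences. Section 3.2 says that roll-out in CAMHS will be sought if PPCP is found efficacious. Section 4.2 also leaves open whether the study is an efficacy trial or a pilot, and these call for different readings of the same estimate.

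**Working it through.** **Inputs.** From section 9.2.1: target difference d = 0.4 SD, equal to 0.16 PACS points; t-test; alpha 0.05; power 80%; attrition 20%. From section 9.2.2: allocation 1:1. From section 4.2: 40 v 40 with 16-week outcomes, and 30-40% of the predicted numbers. Sidedness is not stated. Two-sided reproduces the protocol's figure; one-sided gives 78 per arm and does not.

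**The protocol's own figures.**
- n per arm = 2(1.960 + 0.842)² / 0.4² = 98.1, rounded up to 99, so 198 in total. This matches.
- 198 / 0.8 = 247.5, rounded up to 248. This matches.
- Exact (noncentral t) power at 99 per arm is 79.97%.

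**The same test at 40 v 40.** The 80 already have 16-week outcomes, so no further attrition is deducted.
- Noncentrality = 0.4 × √(40/2) = 1.789 on 78 df. Power = 42.4% (43.2% by the normal approximation).
- 30-40% of 248 is about 37 to 49 per arm. Power = 40% to 50%.
- Effect detectable with 80% power: (1.960 + 0.842) × √(2/40) = 0.626 SD by the normal approximation, 0.634 SD exactly.
- Implied SD = 0.16 / 0.4 = 0.40 points, so the detectable effect is 0.634 × 0.40 = 0.25 points, against the target of 0.16.
- 95% CI half-width = t(0.975, 78) × √(2/40) = 1.991 × 0.2236 = 0.445 SD, or 0.18 points.

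An observed difference of zero would therefore have an interval of ±0.445 SD, which includes 0.4 SD.

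**Sensitivity to covariate adjustment.** Let R be the correlation of the ANCOVA covariates with the outcome. The protocol gives no value, so R is assumed. The residual SD shrinks by √(1 − R²), with 74 df taken for the error term.

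| Assumed R | Power for 0.4 SD | p if 0.4 SD is observed |
|---|---|---|
| 0.3 | 46% | 0.065 |
| 0.4 | 49% | 0.055 |
| 0.5 | 53% | 0.042 |
| 0.6 | 60% | 0.028 |
| 0.7 | 70% | 0.014 |
| 0.8 | 84% | 0.004 |

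Power stays below 80% unless R is close to 0.8. The half-width falls below 0.4 SD once R exceeds about 0.44.

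**The case against.** The strongest reply is that nothing is hidden. Section 4.2 states the shortfall, gives 40 v 40 and itself suggests the pilot label. A protocol properly keeps its design calculation, and 198 and 248 are right. All of this stands. The point is therefore a superseded statement left as current; a reader who infers an arithmetic error or concealment would be wrong.

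The achieved power or precision could sit in the statistical analysis plan, and the figure in section 4.2, which was not available for this check, may show the number randomised. That is fair, and absence of these figures from the protocol would be a weak point alone. It does not excuse stating 248 and 80% power as the current aim.

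A reader might also infer that an observed effect equal to the 0.4 SD target could not be significant. That holds for the unadjusted t-test (t = 1.789, p = 0.078, 95% CI −0.05 to 0.85 SD). The amended analysis is an ANCOVA, and at R of about 0.44 or more the same estimate would be significant. The documents do not settle R.

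Finally, section 9.2.1 calls 0.4 SD conservative and cites an earlier trial with 1.06 SD, at which 40 v 40 has 99.7% power. So the power is low for the protocol's chosen target, not for every plausible effect.

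**Conclusion.** The point holds. The size and power stated as current in the Study Summary and section 9.2.1 are not those of the trial to be analysed. For 0.4 SD, power is about 42% on the protocol's own test (40-50% across its 30-40% range) and about 53-70% with R assumed to be 0.5-0.7. On the unadjusted test, a null estimate cannot exclude the difference that section 9.2.1 calls clinically significant. The raw-scale figures assume the implied SD of 0.40.

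Three stronger readings are not supported:
- That no feasibility aim exists. Section 7.3 lists feasibility of delivering both interventions among the process-evaluation aims.
- That the waitlist power undermines the objective in section 3.1 to "Conduct a full RCT to establish whether the personalized approach is superior to parent-led education and support". That sentence concerns PPCP v PLES, a different contrast, for which section 4.2 already warns that analyses may be only descriptive.
- That a significant result must overstate the effect. Significant estimates average about 1.5 times the truth if the true effect is exactly 0.4 SD, but about 1.12 times at 0.63 SD, with no inflation at 1.06 SD.

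**What to change.** - In the Study Summary and section 9.2.1, mark 248 dyads and 80% power as the original, superseded target, as section 7.1.1 already does for the analysis.
- Beside it, state the number randomised, the number with 16-week PACS, the power now available for 0.4 SD (42% unadjusted, or an adjusted figure with its assumed correlation) and the expected CI half-width (about 0.45 SD unadjusted).
- In section 4.2, settle before the 16-week data are unblinded whether the PPCP v waitlist result will be reported as an under-recruited efficacy comparison or as a pilot. In either case, commit to reporting the estimate with its 95% CI and to not reading non-significance as absence of effect.

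The cost is an amendment to wording and a less favourable stated power. It needs no further recruitment and no change to the data or the analysis model.

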# 9.2.2 Randomisation procedures and blinding arrangements

Randomisation of parent/child dyads to waitlist/PLES or PPCP trial arms will be at the individual dyad level with 50% of dyads randomised to either arm. Within parent subpopulation ("decliners" or "non-responders to group approaches") we will use randomly varying block sizes to ensure that the times when dyads start on their allocated groups also balances across trial arms. Randomisation will be provided online vis an independently monitored computer system set up by the accredited Clinical Trials Unit at King's College (KCTU).

The procedure is as follows: Each participant will be allocated a unique, anonymised ID number King's College London Clinical Trials Unit. Details will be entered into the KCLTU randomisation system. The outcome of allocation will be communicated to the trial's senior clinical supervisor, [name], who will then arrange for either a PPCP therapist (intervention arm) or PLES therapist (comparison arm) to make contact with the allocated participant in order to communicate the next steps.

Other members of the research team (including the Chief Investigator, senior statistician and research assistants) will remain blind to participant allocation status throughout the trial. As a result of the change in study design and the analyses of 16-week outcome data before locking the 32 week data collection blinding it is now only possible for the 16-week outcome collection and analyses to remain blind, but not for any 32-week outcome data.

